Preliminary studies have evaluated the use of a novel new biologic scaffold material that functions as a degradable extracellular matrix (ECM) that supports the regeneration of injured or missing tissue called Gentrix. This biologic scaffold material is composed of an extracellular matrix derived from porcine small intestine and urinary bladder and has been shown to promote site-specific, constructive tissue remodeling in preclinical and clinical applications for a number of body systems including the esophagus(Nieponice et al.). This Urinary Bladder Matrix (UBM), acts by recruiting native stem cells and progenitor cells to the extracellular matrix material, thus promoting regeneration of native tissue and site-specific remodelling in a process that includes complete degradation of the scaffold in 60-90 days with resultant reconstruction of tissues devoid of inflammation or scar tissue(Nieponice et al.). ACell currently markets UBM under the brand-name of Gentrix. We propose the use of ACell Gentrix Surgical Matrix PSM ("Gentrix PSM") for reinforcement of esophageal anastomoses in patients undergoing esophagectomy, proximal gastrectomy (PG) or total gastrectomy (TG). We hypothesize that by providing a biologic scaffold at

the site of anastomosis and healing tissue, this will enhance the integrity of native tissue and promote regeneration, reducing the incidence of anastomotic leak without causing stricture.

Patient Population:

All patients who are scheduled to undergo potentially curative esophagectomy, proximal gastrectomy or total gastrectomy for cancer at Memorial Sloan-Kettering Cancer Center and participating sites will be approached to participate in the study.

Design:

Patients undergoing esophagectomy, PG or TG, via open or minimally-invasive approach, will receive a standard anastomosis reinforced with Gentrax PSM placed extraluminally. Patients would then be followed postoperatively for evidence of anastomotic leak. One routine contrast swallow study with barium, Gastrografin or Omnipaque will be performed at postoperative day 4-10. Leaks will be recorded both radiographically and clinically. Patients will continue to be followed for 90 days +/- 14 days postoperatively for evidence of stricture formation, a secondary endpoint of the study.

Time to Completion:

We plan to accrue 86 patients 76 of which will be accrued at MSK. We expect that accrual will last about 20 months. With follow up of 90 days (+/- 14 days) to evaluate for stricture, we expect the total study time will be 24 months.

2.1 OBJECTIVES AND SCIENTIFIC AIMS

Primary Objective:

1. To determine if reinforcement of esophageal anastomoses with Gentrax PSM decreases the rates of anastomotic leak. Anastomotic leak will be assessed by clinical observation and one postoperative contrast study (thin-barium, Gastrografin or Omnipaque swallow) on postoperative day # 4-10.

Secondary Objective

1. Assess stricture formation clinically and by determination of dysphagia score at 90 days postoperatively.
2. Examine cost metrics associated with all patients enrolled.

3.1 BACKGROUND AND RATIONALE

3.2 Overview

Bowel resection and anastomosis are among the most carefully taught and heavily investigated procedures performed by surgeons. The goal is to restore intestinal continuity after resection of a portion of the bowel, enabling resumption of normal bowel function. Despite multiple efforts to optimize surgical technique over decades, including careful tissue handling, adequate mobilization to minimize tension, efforts to maximize blood supply, postoperative nasojejunal decompression, and development of improved stapling devices, devastating complications of anastomotic leak and stricture formation still occur and incidence rates have not been significantly reduced(Doglietto et al.). The esophagus differs from other segments of the GI tract in that it lacks an outer serosal layer, which is the true strength layer in other segments. Additionally, the blood supply of the esophagus is segmental in nature without the high degree of anastomotic flow as is present in the stomach and small and large intestine. Esophagogastric anastomoses are therefore particularly high-risk, with leak rates varying widely in the literature and ranging up to 26% reported in the literature(Kim and Takabe; Neutzling et al.; Pacelli et al.). At our institution, leak rate is currently between 8-15% (per verbal communication with [name] and [name] based on our institutional esophageal and gastric databases).

Anastomotic leaks are defined both clinically and radiographically. A clinical leak is defined by the appearance of enteric contents in an operatively-placed drain near the anastomosis or in a percutaneous drain placed post-operatively to evacuate a peri-anastomotic collection. A radiographic leak is one detected on cross-sectional imaging or by a contrast swallow study showing extravasation of oral contrast at the anastomosis. While patients undergoing bowel resection for benign disease are at risk of anastomotic leak, those undergoing surgery for cancer are at even greater risk as they often have poor nutrition and are subject to perioperative chemotherapy and radiation therapy. Anastomotic leaks result in prolonged hospitalization, immense health care costs, repeat procedures, and decreased quality of life, and in cancer patients, decreased survival(Yoo et al.). Patients who experience an anastomotic leak have 3x higher perioperative mortality than those who do not. Of those who survive the perioperative period, their long-term survival is also drastically reduced compared to patients who do not experience a leak(Mitchell).

Current techniques for esophageal anastomosis include hand-sewn and stapled closures with linear or circular stapling devices. Stapled closures are generally end-to-side if circular staplers are employed or side-to-side if linear staplers are used. Use of a linear stapler results in a remaining defect that must be sutures closed. All of these techniques are acceptable and choice depends on surgical approach and surgeon preference. No single technique has been definitively shown to be superior to the others.

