9.2 Management common to both groups

There are no restrictions on preoperative antibiotics, approach (laparoscopic or open), incision, and extent of lymph node dissection, margins, or other features of the

resection: the surgeon should proceed as he or she normally would in the absence of the trial. Most surgeons at MSKCC perform stapled gastrointestinal anastomoses but the type of primary anastomosis performed (stapled or hand-sewn) would be left to the discretion of the surgeon. Similarly, surgeons have the discretion to use nasogastric tubes or drains if they desire. Patients would undergo standard oncologic resection of their tumor by esophagectomy, PG or TG depending on site of disease. Patients with clinical evidence of advanced disease may undergo an initial laparoscopy procedure to evaluate for metastases prior to resection. Patients found to have metastatic disease would not undergo resection and would not be eligible for the study. Up to this point in the treatment course, all procedures would have been routine.

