9.3 Anastomotic reinforcement with ACell Gentrix PSM

All esophageal anastomoses will be reinforced circumferentially with ACell Gentrix PSM. The material will be secured with ~ 2 cm overlap of the material proximal and distal to the anastomosis (see below).

ACell Gentrix PSM shown wrapped circumferentially around an esophagojejunal anastomosis with anchoring stitch after total gastrectomy reconstruction.

After anastomotic reinforcement, the procedure will be completed in a routine fashion with final assessments for hemostasis, drain placement when indicated, and wound closure.

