10.1 EVALUATION DURING TREATMENT/INTERVENTION

Clinical assessment for anastomotic leak will be carried out during the course of the hospitalization after surgery and up to 90 days +/- 14 days postoperatively. One radiographic assessment for leak will be performed during the interval from postoperative day 4-10. The grade of leak will be assigned according to standard criteria. For patients who die in the first 120 days following surgery where no documentation of leak has occurred, a request for autopsy will be made to determine the cause of death and will clarify whether or not a leak had occurred.

Clinical assessment for stricture will take place at 90 days +/- 14 days postoperatively. Patients will be evaluated in the outpatient clinic and will be assigned a dysphagia score from 0-4 by the RSA or clinical staff based on the following scale:

- 0 – Able to eat a normal diet
- 1 – Able to eat some solid food
- 2 – Able to eat semisolids only
- 3 – Able to swallow liquids only
- 4 – Unable to swallow anything

A dysphagia score of ≥ 2 will prompt further work up with upper endoscopy and possible dilatation if stricture is identified.

Patients may also be called by a member of the research team check on their health status until the study closes. This will allow for more robust data to be collected on the long term affects of the Gentrix implantation.

Data for cost metrics will be collected postoperatively through POD90 (+/- 14 days). These include metrics such as Length of Stay, Readmission, Complications, Reoperation and Total Hospital Bill. Total hospital bill data will be obtained from the Physician Billing Department. Data will be collected for all 86 patients enrolled and summarized. Cost of total hospital bill will be determined from the date of admission on protocol to day of discharge on protocol. Additional cost of re-admission to day of discharge of re-admission will so be included.

Examination/Intervention	Preop Visit(s)	OR	POD 4-10	POD21 (+/- 7 days)	POD90 (+/- 14 days)	Every 3 months until the study closes
Obtain Informed Consent	X					
Relevant / Interim Medical History	X			X	X	
Physical Exam	X					
Pre Surgical Testing	X					
Surgery		X				
Implantation of Gentrix PSM		X				
Thin-barium or Gastrografin Swallow Evaluation			X			

Dysphagia Score				X	
Symptom Assessment			X	X	
AE Assessment	X		X	X	
Review of the patient's medical record					X

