12.0 CRITERIA FOR THERAPEUTIC RESPONSE/OUTCOME ASSESSMENT

The primary outcome of the trial is the rate of anastomotic leak after reinforcement of esophageal anastomoses with Gentrix PSM. Esophageal anastomotic leaks will be determined by one routine postoperative contrast swallow study on 4-10 as well as clinical course. Anastomotic stricture formation occurs later in the postoperative period and will be diagnosed based on symptomatology. Patients reporting symptoms consistent with stricture will be evaluated with radiographic contrast swallow study or endoscopy.

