14.0 BIOSTATISTICS

The historical control leak rate at our institution among patients receiving partial, total gastrectomy or esophagectomy is 8-15%: esophagectomy leak rate of around 15% and total and proximal gastrectomy leak rate of around 10%. A weighted average of 13% between the groups will be considered an unacceptable leak rate. We will employ Simon's two stage design to show a decrease in the leak rate assessed radiographically and clinically from 13% to 5% which would require 86 total patients to detect this difference with type I and II error rates of 10% each. In the first stage we will enroll 43 patients and if 5 patients experience a leak, then the study will be terminated, however if only 4 or less patients experience a leak then we will proceed to accruing up to 86 patients. If at the end of the second stage we see 7 or less leaks then we will consider the study worthy of further investigation. We expect two thirds of the accrued patients to have total gastrectomy performed while the rest to receive esophagectomy. Exact 95% confidence intervals will be computed for the leak rate for all the patients as well as separately for esophagectomy and total gastrectomy.

Similarly, the stricture rate will be estimated using binomial proportions and exact 95% CI will be computed.

The different cost metrics will be summarized descriptively: continuous cost metrics will be summarized using medians and ranges while binary variables will be summarized using binomial proportions.

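### Does the drain-or-imaging wording in Section 3.2 leave some leaks out of the primary endpoint?

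*Combined protocol and SAP*

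**What the plan says.** Section 3.2 (Overview, under Background and Rationale) describes two kinds of leak. The clinical kind is given as "A clinical leak is defined by the appearance of enteric contents in an operatively-placed drain near the anastomosis or in a percutaneous drain" that is placed after surgery to empty a collection near the anastomosis. For the other kind the text is "A radiographic leak is one detected on cross-sectional imaging or by a contrast swallow study showing extravasation of oral contrast at the anastomosis". Neither sentence carries a time limit.

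The sections that govern assessment and analysis are worded differently:

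- Section 2.1: "Anastomotic leak will be assessed by clinical observation and one postoperative contrast study", the study falling on postoperative day 4-10.
- Section 10.1: clinical assessment during the hospital stay and up to day 90 (+/- 14). For deaths in the first 120 days with no documented leak, "a request for autopsy will be made to determine the cause of death and will clarify whether or not a leak had occurred".
- Section 12.0: leaks "will be determined by one routine postoperative contrast swallow study on 4-10 as well as clinical course".
- Section 14.0: a two-stage design to "show a decrease in the leak rate assessed radiographically and clinically from 13% to 5" per cent. It continues at 4 or fewer leaks in 43 patients and succeeds at 7 or fewer in 86.

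Drains are optional. Section 9.2 says "surgeons have the discretion to use nasogastric tubes or drains if they desire", and Section 9.3 has "drain placement when indicated". None of Sections 2.1, 10.1, 12.0 or 14.0 refers back to Section 3.2.

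**The concern.** Section 3.2 is the only place that says what a leak is, and it names drain contents, cross-sectional imaging and contrast swallow. Operative drains are at the surgeon's discretion and only one swallow is scheduled. A patient whose leak was seen directly at reoperation or endoscopy, drained through the wound, or was found at autopsy could therefore meet neither category. That sits badly with Section 10.1, where autopsy is meant to settle whether a leak occurred. The windows differ as well: clinical assessment ends by day 90 + 14 = 104 at the latest, while autopsy is requested for deaths up to day 120.

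The decision rests on small counts, and there is no control arm to share a counting rule with. If the historical 13% included leaks that the trial did not count, the comparison would favour the device. Two assessors, one using Section 3.2 and one using Section 12.0, could also classify the same patient differently.

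**Working it through.** **1. Reproduce the design.** Inputs from Section 14.0: n1 = 43, continue at 4 or fewer leaks; n = 86, success at 7 or fewer; rates 13% and 5%; both error rates 10%. With counted leak rate q,

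P(success | q) = sum over x = 0 to 4 of Bin(x; 43, q) × P(Bin(43, q) ≤ 7 − x).

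- q = 0.13: 0.0989, so type I error is 9.9%.
- q = 0.05: 0.9012, so power is 90.1%.

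The plan's figures hold.

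**2. What would the literal wording miss?** Take each route in turn.

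| How the leak is found | Section 3.2 read literally | Sections 2.1, 10.1, 12.0, 14.0 |
|---|---|---|
| Scheduled swallow | counts | counts |
| Later swallow or cross-sectional imaging | counts (no time limit) | counts as part of the clinical follow-up |
| Reoperation, with a drain then showing enteric contents | counts (a drain placed at any operation fits the words) | counts |
| Direct view at reoperation or endoscopy, no drain output, no positive imaging | not listed | counts as clinical course |
| Wound drainage only | not listed | counts as clinical observation |
| Autopsy only | not listed | Section 10.1 uses it for this purpose |

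Section 1.0 describes reoperation for a leak as including drain placement, so the third row is a likely route for reoperated patients. The gap is limited to the last three rows, and there the assessment sections supply the answer.

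**3. Size if the literal wording were used and the benchmark were broader.** The documents give no share of leaks lacking both drain and imaging evidence, so f is an assumption. Set q = 0.13 × (1 − f). Expected leaks at 13% are 86 × 0.13 = 11.18.

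| Assumed f | Leaks missed (11.18 × f) | q | P(success) at true 13% |
|---|---|---|---|
| 0 | 0 | 0.1300 | 0.099 |
| 0.02 | 0.22 | 0.1274 | 0.111 |
| 0.05 | 0.56 | 0.1235 | 0.132 |
| 0.10 | 1.12 | 0.1170 | 0.172 |

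**4. The opposite case.** Suppose instead that the trial counts more broadly than the benchmark. This is also an assumption.

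| Counted rate | P(success) |
|---|---|
| 13% counted as 14% | 0.062 |
| 13% counted as 15% | 0.037 |
| 5% counted as 6% | 0.811 |
| 5% counted as 7% | 0.694 |

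Here the error runs against the device. Sections 1.0 and 3.2 attribute the historical 8-15% to verbal communication from institutional databases and give no leak definition, so the documents do not show which case applies, or whether either does. If trial and benchmark are counted alike, the figures in step 1 stand.

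**The case for a change.** The strongest case for acting is that Section 12.0 is where an endpoint definition belongs and it does not contain one. If Section 3.2 is only background, then nothing defines the primary endpoint. If it is binding, Section 10.1's use of autopsy has no place in it. A single leak separates 7 from 8 in 86, or 4 from 5 in 43, and the pilot's 1 in 28 (Section 3.3) is described as a clinical leak only, a different scope from the trial's endpoint.

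Part of this stands. The wording is loose and spread over several sections, and the definition behind the benchmark is not given. But loose wording is not a rule that excludes cases. On the clinical side, Sections 2.1 and 12.0 are vaguer than Section 3.2 rather than opposed to it, and the autopsy request makes sense only if its result is used. The difference between day 104 and day 120 need not be a conflict: one is an assessment window, the other a request meant to uncover an undocumented leak, and an autopsy after day 104 may reveal an earlier one. Sensitivity to one event at the boundary is a property of any threshold rule of this size. Writing out the widest possible list would not secure comparability either while the benchmark's own rule is unknown; step 4 shows that it could cost power.

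**Conclusion.** The concern does not hold as a defect requiring a change. It is a gap in detail that analysts can fill sensibly. The omission appears only if descriptive background prose is treated as exhaustive and allowed to override the sections on assessment and analysis. Followed as written, those sections lead an assessor to count a leak established by clinical course or autopsy as well as by drain or imaging.

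The design reproduces at 9.9% type I error and 90.1% power. The illustrated range at a true 13% (11.1% to 17.2% false success) needs two things the documents do not show: a benchmark counted more broadly than the trial, and 2% to 10% of leaks with neither drain nor imaging evidence. The reverse assumption moves the result the other way. This conclusion rests on reading Section 3.2 as background. It would be different if the case report forms, which are not among the documents, restricted leaks to drain or imaging evidence. Anyone interpreting the final count should remember that the definition behind the historical rate is unknown.

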3.3 Preliminary Data

We have performed a pilot study of 28 patients undergoing total gastrectomy via open or minimally-invasive approach to determine the feasibility of extraluminal reinforcement of the esophagojejun al anastomosis with Gentrax. In this series of patients we determined that this technique is feasible in both open and minimally-invasive procedures and that it adds essentially no time to the procedure and introduces no toxicity or side effects. Of the 28 patients, 1 experienced a clinical anastomotic leak for a rate of 3.6%.

3.4 Study Rational / Purpose

Given the feasibility of this technique and the encouraging preliminary results, the current study is proposed to determine if reinforcement of esophageal anastomoses with ACell Gentrix PSM will reduce the rate of esophageal anastomotic leak.

4.1 OVERVIEW OF STUDY DESIGN/INTERVENTION

4.2 Design

Eligible patients at MSKCC and participating sites who are candidates for curative resection of esophageal or gastric cancer (requiring total gastrectomy (TG), proximal gastrectomy (PG) or esophagectomy) will be consented pre-operatively. Patients will undergo standard resection and gastrointestinal anastomosis and will then have reinforcement of the anastomosis with Gentrix PSM. Patients undergoing esophagectomy, PG or TG will be evaluated with one routine postoperative contrast swallow study at post-operative day #4-10.

4.3 Intervention

Surgical intervention will proceed in standard fashion via open or minimally-invasive approach. If a minimally-invasive approach is utilized, the Gentrix will be inserted through the 10-12 port and prepared for laparoscopic insertion according to approved measures. Gastrointestinal anastomoses would be performed in standard fashion with stapled technique or hand-sewn, followed by reinforcement by wrapping the anastomosis circumferentially with a strip of Gentrix Surgical Matrix PSM 4x12cm (PSM0412). The material would be positioned with the lamina propria surface apposed to the anastomosis itself and the basement membrane surface facing out. The cuff of Gentrix PSM would then be tacked in place with interrupted absorbable sutures.

5.1 THERAPEUTIC/DIAGNOSTIC AGENTS

5.2 Background

ACell Gentrix devices are an extracellular matrix scaffold derived from porcine urinary bladder matrix (UBM). The bladder is harvested and processed to remove the muscular and submucosal tissue layers. UBM is disinfected, packaged, and sterilized via electron beam radiation. This yields a non-crosslinked, completely resorbable, acellular extracellular matrix scaffold, containing naturally-occurring collagens and proteins and maintains an epithelial basement membrane surface.

UBM is unique in that it contains a collection of proteins arranged in a natural three-dimensional structure unlike other synthetic materials. UBM maintains an epithelial basement membrane, and contains numerous collagens, laminin, growth factors, and glycosaminoglycans.

UBM was tested against liver and small intestine ECM scaffolds, which unlike UBM do not contain a surface with composition and morphology consistent with that of an intact basement membrane complex. The UBM basement membrane complex survives processing, and the structure was shown to modulate in vitro cell growth patterns.

The UBM intact basement membrane surface is theorized to contribute to epithelial and progenitor cell attachment and proliferation. The lamina propria surface may promote integration of host connective tissues from the wound bed into the scaffold.

Previous work has shown that the UBM completely incorporates into the surrounding tissue and modulates the healing process which leaves new tissue where scar tissue formation is normally expected. The result is constructively remodeled, site-specific tissue for a variety of medical procedures. UBM is an acellular material and therefore does not lead to pronounced inflammation at the implantation site as shown in dog models and in humans. UBM was demonstrated to facilitate esophageal healing after full-thickness resection in dogs and after extensive endoscopic mucosal resection in humans (Badylak et al.; Nieponice et al.). In the work by Badylak, patients underwent intra-luminal placement of Gentrax after ECM and follow up endoscopies were done at 2 weeks, 5 weeks, 10 months and 13 months post surgery. The entire resected area was covered by normal esophageal epithelium without stricture formation. See image below.

Additionally, an abstract has been published by SAGES (Society of Gastrointestinal Endoscopic Surgeons) in which a series of 3 patients has full-thickness esophageal reconstruction with a patch esophagoplasty using Gentrax with no stricture or clinically relevant leak followed out to one year (Nieponice, 2012).

[figure not shown]

Image 5.1.1 – Badlyak et al. - representative endoscopic views of each stage in the procedure and follow-up.

ACell Gentrax Surgical Matrix PSM is a commercially available device that has been cleared for marketing by the FDA for implantation to reinforce soft tissue where weakness exists in urological, gynecological, and gastrointestinal anatomy including, but not limited to the following procedures: pubourethral support, tissue repair, body wall repair and esophageal repair.

